### Study Setting and Participants:

Children aged 2 to 20 years with a known history of asthma who presented to the Emergency Department at Women and Children's Hospital of Buffalo/Oishei Children's Hospital between April 2015 and March 2018 with an acute exacerbation of mild or moderate asthma were eligible for the study. Asthma severity was defined by Pediatric Asthma Scores[2, 12] (PAS). Mild asthma is defined as: PAS of 5 to 7; Moderate asthma is defined as: PAS of 8 to 11; Severe asthma is defined as: PAS of 12 or more. History of asthma is defined by physician diagnosis of at least one prior episode of wheezing which responded to beta agonists. Patients were excluded from the study if they had signs of severe asthma exacerbation (PAS of 12 or more), had used oral steroids in the last 2 weeks, had chronic lung disease (e.g., cystic fibrosis), had been given parenteral steroids, or if they vomited two doses of oral steroids in emergency department.

Research assistants screened asthma patients through the electronic medical record between the hours of 8 a.m. and 11 p.m. 7 days a week. Patients were approached sequentially based on registration time. If a patient appeared to meet study criteria, his/her ED treating physician was approached by the research assistant for identifying patient's eligibility. If a patient was fully eligible, the legal guardian and/or patient were approached for consent.

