#### Analytic Plan:

Descriptive characteristics were computed for all patients combined and separately by dexamethasone group assignment. Categorical variables were reported as proportions in percentage, and continuous level variables as means and standard deviations. Separate independent t-tests were used to assess differences by group for post-discharge outcomes of interest including days for symptoms to resolve. Separate binary logistic regression adjusting for age, gender and severity of exacerbation were conducted to assess group differences in post-discharge outcomes including patients who had a return visit for unresolved asthma symptoms (ED, primary care or urgent care), days to symptom resolution, any missed school days between discharge and follow-up, rates of vomiting, and side-effects (changes in appetite, insomnia, mood swings); odds ratios with 95% confidence intervals were reported. Similar analyses were conducted to compare events and side effects between Groups 1 and 2 by asthma severity, using an intention-to-treat approach. Based on our clinical experience, we based our a-priori sample size calculation on an estimated non-inferiority limit of 11% and a rate of 12% return for asthma for each group. With a power of 80% and alpha of 0.05, a minimum sample size of 216 (108 subjects per group) was determined. All statistical tests were two-tailed, and analyses conducted with SYSTAT 13 (SYSTAT Software, 2004).

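### No sparse-data method is planned for the vomiting, side-effect and by-severity odds ratios, which may have no finite estimate if an outcome occurs in about 5% of patients or fewer

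*Combined protocol and SAP*

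**What the plan says.** The Analytic Plan section sets out the model: "Separate binary logistic regression adjusting for age, gender and severity of exacerbation were conducted to assess group differences in post-discharge outcomes". With treatment group included, that is four terms. The listed outcomes are return visits, days to symptom resolution, missed school days and, at the end, "rates of vomiting, and side-effects (changes in appetite, insomnia, mood swings); odds ratios with 95% confidence intervals were reported".

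The comparison is then repeated by severity: "Similar analyses were conducted to compare events and side effects between Groups 1 and 2 by asthma severity, using an intention-to-treat approach". The within-severity model is not described further. Study Setting and Participants defines the two enrolled levels, "Mild asthma is defined as: PAS of 5 to 7; Moderate asthma is defined as: PAS of 8 to 11", and excludes severe exacerbations.

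The only event rate given is for return visits, in the sample-size assumptions: "estimated non-inferiority limit of 11% and a rate of 12% return for asthma for each group". The documents give no expected rate for vomiting, appetite change, insomnia or mood swings, and no expected mild/moderate split. They name no penalised, exact or other sparse-data method.

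**The concern.** If one treatment arm has no events, maximum likelihood pushes the treatment odds ratio to zero or infinity, and the usual 95% interval does not exist in any useful sense. If neither arm has events, the odds ratio is undefined. Software may still print a very large coefficient with a huge standard error, which can pass for a result.

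The analyses most exposed are tolerability outcomes and, above all, tolerability within severity groups, where the sample is divided. Comparing one dose with two makes tolerability a natural question. Without a stated fallback, the method for an empty arm would be chosen after the counts were known.

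The by-severity analyses raise a smaller, related matter. If severity enters as mild/moderate, it is constant within a severity group and cannot be fitted there. The plan does not say what replaces it.

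**Working it through.** **Inputs from the documents.** 108 per group, 1:1 allocation, a 12% return-visit rate, a margin of 11 percentage points, 80% power, alpha 0.05, and two enrolled severity levels.

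**Inputs assumed.** Event rates of 5%, 3% and 2% for an uncommon outcome, equal in both arms. Severity-group sizes of 54 per arm (even split, 108/2) and 32 per arm (smaller group of a 30/70 split, 0.30 × 108 = 32.4). Full follow-up and equal arms within each severity group are also assumed.

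**The plan's own figure.** "With a power of 80% and alpha of 0.05, a minimum sample size of 216 (108 subjects per group) was determined". The unpooled non-inferiority formula gives n = 2 × 0.12 × 0.88 × (1.645 + 0.842)² / 0.11² = 107.9, so 108 per arm and 216 in total. This match uses one-sided alpha 0.05; one-sided 0.025 gives 137 per arm. How that fits with two-tailed testing is a separate matter and does not affect this point.

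**Expected return visits.** 0.12 × 216 = 25.9 overall, and about 13 in one of two equal severity groups.

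**Chance of an empty arm.** With m patients per arm and event rate p, one given arm has no events with probability q = (1 − p)^m. At least one of two arms is empty with probability 1 − (1 − q)². For example, with m = 54 and p = 0.05, q = 0.95^54 = 0.0627 and 1 − 0.9373² = 0.121.

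| Rate p | 108 per arm (overall) | 54 per arm (assumed) | 32 per arm (assumed) |
|---|---|---|---|
| 12% (stated, return visits) | about 0 | 0.2% | 3.3% |
| 5% (assumed) | 0.8% | 12% | 35% |
| 3% (assumed) | 7% | 35% | 61% |
| 2% (assumed) | 21% | 56% | 77% |

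**What an empty arm does.** Take invented counts of 0/54 against 3/54 in one severity group, unadjusted.

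- Ordinary maximum likelihood does not settle: the log odds ratio reaches about 18 to 19 with a standard error of about 4,500 to 7,200, depending on the number of iterations.
- Firth's method in a 2×2 table equals adding 0.5 to each cell: (3.5 × 54.5)/(51.5 × 0.5) = 7.4. The standard error of the log odds ratio is √(1/3.5 + 1/51.5 + 1/0.5 + 1/54.5) = 1.52, giving a Wald 95% interval of 0.37 to 147.
- The exact conditional 95% interval runs from 0.42 to infinity.
- The risk difference is 3/54 − 0 = 5.6 percentage points. The Wilson intervals are 1.9% to 15.1% for 3/54 and 0 to 6.6% for 0/54. Newcombe's limits are therefore 5.6 − √(3.65² + 6.64²) = −2.0 and 5.6 + √(9.55² + 0²) = 15.1 percentage points.

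The penalised and score methods give wide but finite answers where the planned model gives none.

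**The case against.** The strongest objection is that nothing in the documents shows these outcomes to be rare. A reader might infer that arms will readily be empty and that the planned odds ratios will fail. The documents do not support that. The one stated rate is 12%, at which an empty arm is negligible overall and unlikely within a severity group of the sizes considered. Some listed outcomes, such as missed school days or mood change, may be common. The stratum sizes are assumed too. The exclusion of patients who vomited two oral steroid doses in the emergency department tends to lower vomiting counts, but it is not a rate. This objection stands, and it is why the point is conditional.

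A reader might also count every failure of the adjusted model, which gives larger figures. An empty sex category, for instance, separates the data as well. But separation on a covariate alone makes that covariate's coefficient diverge; it does not by itself make the treatment odds ratio infinite. Only empty treatment arms are counted here.

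Third, the plan says only "Similar analyses were conducted to compare events and side effects between Groups 1 and 2 by asthma severity". That does not commit it to an identical model, dropping a constant term is the obvious step, and severity could have entered as the PAS score, which was collected. This stands: the constant term is a matter of wording and does not harm the treatment estimate.

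Finally, a one-line fallback to an exact or penalised method when a cell is empty would close the basic gap. That is fair. Naming the method for these models in advance has the further merit that the choice does not depend on the counts.

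**Conclusion.** The point holds as a conditional gap in the plan and is a minor improvement. For an outcome at about 5% or below, the chance that the treatment odds ratio has no finite estimate or interval is small over the whole trial (about 1% at 5%, 7% at 3%). Within a severity group it is material: 12% and 35% with 54 per arm, 35% and 61% with 32 per arm. For an outcome near 12% the planned model is rarely in difficulty for this reason.

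These figures rest on assumed rates, assumed severity splits, equal rates in the two arms and complete follow-up. Losses at the day 6 telephone call would shrink the arms and raise the chances. The point concerns vomiting, side effects and the by-severity comparisons. It does not touch the basis of the sample size or the overall return-visit comparison.

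**What to change.** In the Analytic Plan, for vomiting, each side effect and every by-severity model:

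- Replace ordinary maximum likelihood with Firth-penalised logistic regression and profile-likelihood 95% intervals.
- Beside each odds ratio, report the event counts by arm and the unadjusted risk difference with a score interval (Newcombe or Miettinen-Nurminen).
- State the within-severity model explicitly: drop the mild/moderate term, which is constant there, or replace it with the PAS score already collected.

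The cost is plan wording, some analysis work and possibly software other than the named package. Odds ratios shrink slightly towards 1. Where events are common, the results will agree closely with the planned analysis. No additional data or patients are needed.

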### Study Protocol:

Block randomization was used to generate a list to be used for subject assignment with a 1:1 ratio of allocation to the single dose group and the two dose group. Demographic information such as age, gender, race, duration of asthma symptoms, number of previous hospitalizations, and current medication was collected. Pertinent exam findings such as patient's vital signs, pulse oximetry, and PAS were also collected along with medications given in the ED.

Group 1 was given 0.6mg/kg (max 16mg) of dexamethasone orally in the emergency department. Group 2 was given the same dose in the emergency department, and then a prescription for a second dose was sent to their pharmacy to be filled and administered at home 24 hours later. We worked with a nearby 24-hour pharmacy to ensure medication availability; however, pharmacy preference was left up to the family. Both groups received asthma treatment following a standardized asthma care path.

All patients were contacted by phone by a research assistant on the 6th day following the emergency department visit. Research assistants were not completely blinded during the study. They were initially blinded to the study group at the start of the phone interviews; however, during the course of the

interview they did ask if the prescription for the second dose of dexamethasone was filled and if the medication was given to the patient. Information collected during the phone interview included additional visits to medical providers (ED, primary care or urgent care) for continued asthma symptoms, information was collected on the reason for visit, whether symptoms continued or worsened, and if additional treatment was needed (scheduled visits and unrelated visits were excluded). School days missed due to asthma exacerbation; length of time symptoms persisted; compliance with the recommended steroid regimen; and any vomiting, side effects or medication administration problems caused by the steroids was also collected.

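### No stated analysis uses the recorded uptake of the second dose, so the as-randomised comparison alone supports a conclusion about prescribing that dose, not about taking it

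*Combined protocol and SAP*

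**What the plan says.** Under Study Protocol, Group 1 has one dose in the emergency department. Group 2 has the same dose, and then "a prescription for a second dose was sent to their pharmacy to be filled and administered at home 24 hours later". On access, the same section says "We worked with a nearby 24-hour pharmacy to ensure medication availability; however, pharmacy preference was left up to the family".

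The day-6 telephone interview records uptake: the research assistants "they did ask if the prescription for the second dose of dexamethasone was filled and if the medication was given to the patient". Its list of items also includes "compliance with the recommended steroid regimen".

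The Analytic Plan then sets out:

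- Summaries by assigned group: "Descriptive characteristics were computed for all patients combined and separately by dexamethasone group assignment".
- Models for outcomes that include return visits: "Separate binary logistic regression adjusting for age, gender and severity of exacerbation were conducted to assess group differences in post-discharge outcomes". Results are odds ratios with 95% confidence intervals.
- Further analyses, described as similar, that "compare events and side effects between Groups 1 and 2 by asthma severity, using an intention-to-treat approach". This is the only place where intention-to-treat (ITT) is named.
- A sample size based on an "estimated non-inferiority limit of 11% and a rate of 12% return for asthma for each group", giving 108 per group.

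None of these names uptake or compliance as a variable, an analysis set or a sensitivity analysis. The non-inferiority limit appears only in the sample-size sentence.

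**The concern.** In a superiority trial, patients who skip the extra treatment usually make the claim harder to reach. In a trial sized for non-inferiority they can make it easier. A Group 2 patient who never takes the second dose has had the Group 1 treatment. If the dose would have helped that patient, the skipping moves the two groups closer together.

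A small as-randomised difference then has two explanations: the second dose adds little, or few families gave it. For someone deciding whether to send a second prescription, the distinction hardly matters, because incomplete uptake is part of what prescribing achieves. For someone asking whether two doses taken are better than one, it matters a good deal. Uptake is what separates the two explanations. It was collected, but the plan does not say that it will be used.

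**Working it through.** **1. The plan's own figure.** Inputs from the Analytic Plan: 12% return in each group, limit 11 points, power 80%, alpha 0.05. With a one-sided 0.05 test,

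n = (1.645 + 0.842)² × 2 × 0.12 × 0.88 / 0.11² = 107.9, so 108 per group and 216 in total.

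This matches, so the limit is an absolute difference in return-visit rates. One-sided 0.025, which corresponds to a 95% interval, would need 137 per group (274).

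**2. How skipping changes the difference.** Assumed for illustration: 23% return on one dose, 12% if two are taken (an effect exactly at the limit), a fraction q of Group 2 skipping at random, and nobody in Group 1 taking a second dose. Then

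- Group 2 rate = 0.12 + 0.11q
- as-randomised difference = 0.11 × (1 − q)

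**3. Chance of meeting the 11-point limit.** The rule, also assumed, is that the Wald upper confidence limit for the risk difference lies below 11 points. The adherence-adjusted estimate is the as-randomised difference divided by the difference in uptake, 1 − q. Meeting the limit on that scale is the same as an as-randomised upper limit below 0.11 × (1 − q). Exact binomial enumeration with 108 per group gives:

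| Skipping q | ITT difference (points) | ITT, 90% CI | Adjusted, 90% CI | ITT, 95% CI | Adjusted, 95% CI |
|---|---|---|---|---|---|
| 0% | 11.0 | 5.2% | 5.2% | 2.8% | 2.8% |
| 10% | 9.9 | 7.8% | 5.3% | 4.4% | 2.6% |
| 20% | 8.8 | 11.2% | 5.2% | 6.6% | 2.7% |
| 30% | 7.7 | 15.4% | 5.3% | 9.5% | 2.7% |

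The rising ITT columns are not errors for the prescribing question, because differences of 9.9, 8.8 and 7.7 points really are inside the limit. They show how often an ITT result would be misread if applied to taking the dose.

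**4. Skippers at different risk.** With q = 20%, a 90% interval and the takers' effect still 11 points:

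- Skippers with a 10% return rate: Group 1 = 0.8 × 0.23 + 0.2 × 0.10 = 20.4%; Group 2 = 0.8 × 0.12 + 0.2 × 0.10 = 11.6%. ITT 12.0%, adjusted 5.4%.
- Skippers with a 36% return rate: 25.6% and 16.8% by the same arithmetic. ITT 10.7%, adjusted 5.1%.

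**5. Price of the adjusted estimate.** Power when return is 12% in both groups:

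| | ITT | Adjusted, q = 10% | q = 20% | q = 30% |
|---|---|---|---|---|
| 90% CI | 80.7% | 72.5% | 64.2% | 54.2% |
| 95% CI | 70.9% | 61.1% | 51.8% | 42.3% |

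The ITT half-width at 90% is 1.645 × √(2 × 0.12 × 0.88 / 108) = 7.3 points. Dividing by 0.8 for 20% skipping gives 9.1 points.

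Simulation with uptake estimated and a delta-method interval agrees. The chance of meeting the limit when the effect equals it is 5.1% to 5.2%, and power is 72.7%, 64.0% and 54.5% (90% interval; 10%, 20% and 30% skipping).

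**6. Over-reported uptake.** If true skipping is 20% but families report 10%, the limit on the ITT scale becomes 0.11 × 0.9 = 9.9 points. The adjusted analysis then meets it in 7.9% of trials, against 11.2% for ITT.

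**The case against.** The strongest reply is that the randomised contrast is a prescribing strategy. Group 2 is defined by being sent a prescription, ITT answers that question validly, and the available text, which opens at Methods, makes no claim about taking the dose. This stands. It makes the point a limit on what may be concluded.

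Three further objections also stand, and they shape the fix.

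- The plan states no risk difference and no confidence-limit rule for return visits, only odds ratios. A risk difference has to be reported before it can be adjusted for uptake.
- The plan reports 95% intervals and two-tailed tests, so power on that basis must be shown. It is about 52% at 20% skipping.
- Uptake and return visits come from the same call. A family not reached probably lacks both, and varying assumed uptake does not supply the outcome.

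Two objections stand in part. Achieved uptake belongs in results, and a compliance summary may have been intended, since the outcome lists are not exhaustive; but no stated analysis links uptake to the comparison. The sizes above are hypothetical: under the plan's own expectation of 12% in both groups, with a dose of no benefit, skipping causes no bias, and the pharmacy arrangement may have limited it. Equal rates are what the trial sets out to test, however, so they cannot be taken as given when interpreting it.

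A reader might infer that ITT is the wrong analysis here, that a per-protocol analysis should replace it, or that many families skipped the dose. The documents support none of these. Patients who take the dose are self-selected, so a per-protocol comparison can lean either way.

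**Conclusion.** The point holds as a limit on interpretation. The second dose depends on families, its uptake is recorded, and no stated analysis uses it. The as-randomised comparison supports a conclusion about leaving the second dose unprescribed. Alone, it does not support a statement about taking two doses rather than one.

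If the true effect of taking the dose were exactly 11 points, 10% to 30% random skipping would raise the chance of meeting the limit from 5.2% to between 7.8% and 15.4% (90% interval), or from 2.8% to between 4.4% and 9.5% (95% interval). These figures rest on assumed skipping rates, an assumed effect at the limit, use of the 11-point limit for a dose that is taken, and 108 complete outcomes per group. At full uptake the two questions coincide.

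The reading that the overall comparison is as-randomised is an inference. Summaries are by assigned group and the by-severity analyses are described as similar, but ITT is named only for the latter. Confidence is medium and the change is advisable: it does not call the ITT result into question.

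**What to change.** 1. State that the return-visit comparison is as randomised. Report its risk difference with a confidence interval against the 11-point limit, beside the odds ratio, and word the conclusion as being about prescribing a second dose.
2. Report the share of Group 2 that took the second dose and the number with unknown uptake.
3. Add one supporting analysis: the as-randomised risk difference divided by the between-group difference in second-dose uptake, with a delta-method or bootstrap interval. As the plan is written in the past tense, label this as added later. Use it, together with uptake, to qualify any statement about taking the dose.
4. Show patients with a known outcome but unknown uptake as takers and then as skippers. For patients not reached, report the number by group and handle their outcome as in the main analysis.

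The cost is one risk difference, one proportion and one ratio with its interval, from data already collected. The ITT result and its power do not change. The supporting estimate has four downsides: a wider interval and the lower power shown above; reliance on telephone reports; the assumption that being prescribed the dose acts only through taking it; and that it describes patients who take the dose when prescribed, not all patients. A per-protocol table is optional, with the caution already given.

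### The by-severity comparison names no treatment-by-severity interaction, so separate results in mild and moderate asthma would not show whether the effect differs between them

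*Combined protocol and SAP*

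**What the plan says.** The Analytic Plan first describes the main models: "Separate binary logistic regression adjusting for age, gender and severity of exacerbation were conducted to assess group differences in post-discharge outcomes". Severity enters there as an adjustment covariate only. The plan then adds that similar analyses, by intention to treat, were used to "compare events and side effects between Groups 1 and 2 by asthma severity".

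Under Study Setting and Participants, the two enrolled categories are given: "Mild asthma is defined as: PAS of 5 to 7; Moderate asthma is defined as: PAS of 8 to 11". Severe exacerbations are excluded, so a by-severity analysis has two strata.

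The sample size rests on "an estimated non-inferiority limit of 11% and a rate of 12% return for asthma for each group", and the plan continues: "With a power of 80% and alpha of 0.05, a minimum sample size of 216 (108 subjects per group) was determined". That calculation concerns return visits in the trial as a whole. The plan also states that all tests are two-tailed. It gives no interaction or heterogeneity test, no multiplicity rule, and no rule for interpreting results by severity. The expected mild-to-moderate split is not given.

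**The concern.** Whether a single dose performs differently in mild and moderate asthma is a question about the difference between two treatment effects. A main model with severity as a covariate assumes one common odds ratio and does not address it. Two separate within-stratum tests do not address it either, because each compares its own effect with zero and neither compares the two effects with each other.

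At stake is the message by severity. A split result could be taken to mean that one dose is enough in one category and not in the other. Two non-significant results could be taken to mean no difference in either. Each stratum holds only part of a sample sized for the overall comparison, so neither conclusion would be supported.

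**Working it through.** **Inputs.** From the Analytic Plan: 12% return rate in each group, 11-point margin, 80% power, alpha 0.05, 108 per group, two-tailed tests. Assumed, because the documents do not give it: half of each arm in each stratum, so 54 per arm per stratum. A 70:30 split (76 and 32 per arm) is shown as a range.

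**1. The plan's sample size.** n per group = (z₁₋α + z₀.₈₀)² × 2p(1−p) / margin².
- One-sided 0.05: (1.645 + 0.842)² × 2(0.12)(0.88) / 0.11² = 107.9, so 108. This matches the plan.
- One-sided 0.025 would give 137, which does not match. The stated size therefore corresponds to one-sided 0.05. The point below does not depend on this.

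**2. Separate two-sided 0.05 tests in the two strata.** If q₁ and q₂ are the chances of significance in each stratum, exactly one is significant with probability q₁(1−q₂) + q₂(1−q₁). The q values come from exact binomial enumeration of the Pearson test.

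| True rates, both strata | Split | q₁, q₂ | Exactly one significant |
|---|---|---|---|
| 12% vs 12% | 50:50 | 0.049, 0.049 | 0.094 |
| 12% vs 12% | 70:30 | 0.051, 0.056 | 0.101 |
| 12% vs 23% | 50:50 | 0.326, 0.326 | 0.440 |
| 12% vs 23% | 70:30 | 0.440, 0.212 | 0.465 |

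A Wald test on the log odds ratio, closer to the planned logistic model, gives about 0.06 with no effect and 0.42 to 0.45 with the common effect. The 12% versus 23% scenario is an illustration (the planning rate plus the margin). In it, nothing differs by severity.

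For comparison, a nominal 5% interaction test falsely signals a difference about 5% of the time per outcome.

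**3. If the margin were also applied within strata.** The plan does not say that it is. Power = Φ(0.11/SE − z₁₋α), with SE = √(2 × 0.12 × 0.88 / n).
- n = 108: SE = 0.0442, power 80.0% (one-sided 0.05).
- n = 54: SE = 0.0625, 0.11/0.0625 = 1.76, power Φ(1.76 − 1.645) = 54.5%. At one-sided 0.025 it is 42.0%.
- n = 32, the smaller stratum at 70:30: 38.6% and 27.2%.

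**4. What the interaction test can do.** On the risk-difference scale, with variances taken at 12% in all four cells, SE = √(4 × 0.12 × 0.88 / 54) = 0.088. For an 11-point interaction, 0.11/0.088 = 1.24, and power is P(Z > 1.96 − 1.24) ≈ 24%.

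On the log-odds scale, take one cell at 23% and three at 12%:
- Ratio of odds ratios = (0.23/0.77)/(0.12/0.88) = 2.19, with log 0.784.
- SE = √(3/(54 × 0.1056) + 1/(54 × 0.1771)) = 0.794.
- Power = P(Z > 1.96 − 0.99) ≈ 17%.

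The interaction test is weak on either scale.

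**The case against.** Several objections carry weight.

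- **How often a split arises by chance.** A reader might infer that chance alone will often make the arms look different in one stratum and not in the other. The documents do not support that. With no true effect, which is the plan's own sizing assumption, a split occurs in only about 9% of trials per outcome, not far above the 5% error of an interaction test. The 44% figure needs a real common effect as large as the full margin.
- **The margin within strata.** A reader might also infer that non-inferiority is to be tested in each stratum. The plan uses the margin only for the sample size. The analyses it describes are t-tests and logistic regressions with odds ratios and 95% CIs. The 55% power figure is therefore conditional on a use that the plan does not state.
- **Intent.** The plan declares no intention to claim different effects by severity, and its sentence could describe a secondary breakdown. Even the within-stratum fit is inferred from terse wording. This makes the matter one of interpretation, but it does not remove it. Comparisons by severity are specified with no interaction and no rule for reading them.
- **The interaction test is underpowered.** This is true. It argues for reporting an estimate with its interval and for limiting claims. It does not make separate tests an answer to the question.

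The overall comparison is unaffected.

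**Conclusion.** The point holds in a limited form. As most naturally read, the plan compares the arms separately in mild and moderate asthma and names no interaction, so its stated method does not show whether the effect depends on severity. The risk of a misleading split is modest with no effect and substantial with a common effect of 12% versus 23%. These figures rest on independent strata, a two-sided 0.05 test in each, and an assumed equal split; a 70:30 split changes them little.

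This bears on the by-severity conclusions only. It is a cheap improvement worth making.

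**What to change.** Replace the separate by-severity comparisons with one logistic model per binary outcome. Fit it on all randomised patients, with group, severity, group-by-severity, age and gender. Report the interaction as a ratio of odds ratios with its 95% CI, and name that scale, because an interaction on the odds-ratio scale need not match one on the risk-difference scale. Show stratum-specific estimates with 95% CIs, labelled descriptive.

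Add two statements to the Analytic Plan:
- No claim of non-inferiority or of no difference will be made within a severity stratum.
- The interaction test has low power (about 24% for an 11-point interaction under equal strata and rates near 12%), so a non-significant interaction does not show equal effects.

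The cost is one model term and a few sentences, using severity data already collected. The small downside is giving up stand-alone stratum claims, which a sample sized for the overall comparison could not support.

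### The trial is sized for non-inferiority on return visits with an 11% limit, but no planned analysis compares anything with that limit

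*Combined protocol and SAP*

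**What the plan says.** Everything on this point is in the Analytic Plan section.

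- **Design target.** The size rests on "an estimated non-inferiority limit of 11% and a rate of 12% return for asthma for each group". The sentence that follows reads "With a power of 80% and alpha of 0.05, a minimum sample size of 216 (108 subjects per group) was determined". Neither says whether the limit is absolute or relative, or whether alpha is one- or two-sided.
- **Analysis.** "Separate binary logistic regression adjusting for age, gender and severity of exacerbation were conducted to assess group differences in post-discharge outcomes", and return visits for unresolved asthma symptoms are one of the outcomes listed. The results are given as follows: "odds ratios with 95% confidence intervals were reported". The other inferential analyses are t-tests for group differences and the same kinds of comparison by asthma severity.
- **Sidedness.** "All statistical tests were two-tailed".

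The limit occurs once, in the sample-size sentence. The available text contains no non-inferiority hypothesis, no interval for a risk difference, no bound set against 11%, and no decision rule.

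**The concern.** A non-inferiority question is answered by showing that the confidence bound for the difference excludes the margin. The planned regression tests whether the groups are equal, and it does so on the odds-ratio scale although the margin works as a difference in percentages. A non-significant odds ratio does not rule out an excess of 11 points, and a non-inferiority claim does not require one.

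The reported intervals could still be held against some margin. But the scale, the confidence level and the cut-off would then be chosen with the results in view. These choices matter here because the level behind the sample size appears to differ from the level used for reporting.

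At stake is the trial's main conclusion, since return visits are the only outcome used for sizing.

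**Working it through.** **Inputs** (Analytic Plan, with 1:1 allocation from Study Protocol): return rate 12% in each group, limit 11%, power 80%, alpha 0.05, 108 per group.

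**1. Reproduce 216.** Unpooled normal formula on the risk difference, true difference zero:

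n per group = (z_α + z_β)² × 2 × 0.12 × 0.88 / margin²

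- Margin 0.11, one-sided 0.05: (1.645 + 0.842)² × 0.2112 / 0.0121 = 107.9, so 108 per group and 216 in total. This matches exactly.
- Margin 0.11, one-sided 0.025: (1.960 + 0.842)² × 0.2112 / 0.0121 = 137.0, so 274 in total.
- Relative margin, 0.11 × 0.12 = 0.0132, one-sided 0.05: about 7,494 per group.
- Two-sided difference test of 12% against 23%: 187 per group, 374 in total.

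The stated size is therefore that of a non-inferiority design with an absolute margin and one-sided alpha 0.05, which corresponds to a two-sided 90% interval.

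**2. Formula power at 108 per group.** SE = √(0.2112/108) = 0.0442, and 0.11/SE = 2.487.

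- 90% interval: Φ(2.487 − 1.645) = 80.0%
- 95% interval: Φ(2.487 − 1.960) = 70.1%

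**3. Exact behaviour of each rule.** All 109 × 109 possible outcomes were enumerated with 108 per group, full follow-up and no covariate adjustment. Ranges cover the Wald, Newcombe and Miettinen-Nurminen intervals.

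| Rule | True 23% (single dose) vs 12%: wrongly passes | True 12% vs 12%: passes |
|---|---|---|
| Two-sided difference test non-significant (pooled z) | 42.5% | 94.8% |
| 90% upper limit of risk difference below 11 points | 5.1-5.2% | 78-81% |
| 95% upper limit of risk difference below 11 points | 2.5-2.8% | 68-71% |

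With an unadjusted Wald test of the odds ratio, the 42.5% becomes 43.2%.

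**4. One concrete case.** Take 13/108 returns on two doses. Any single-dose count from 13 up to 23/108 is non-significant, yet at 23/108 the Newcombe upper limit is 17.6 points (90%) or 19.2 points (95%). The limit stays below 11 points only up to 16/108 (90%) or 14/108 (95%).

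**5. Can the planned odds-ratio interval stand in?** At a 12% reference rate the margin is (0.23/0.77)/(0.12/0.88) = 2.19. The same odds ratio means 8.0 points at an 8% reference rate and 15.4 points at 20%, so it tracks the margin only if the assumed rate is right. Requiring the upper limit to be below 2.19 has 46% power at equal 12% rates with a 95% interval, against 68-71% for the risk difference. With a 90% interval it has 58%, against 78-81%.

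**The case against.** The strongest reply is that nothing in the plan says a non-significant result will be called non-inferior. The 42.5% therefore describes a misuse that the plan does not propose, and only at one pair of true rates. That is correct, and the figure is conditional. The defect does not depend on it, because the sizing hypothesis has no test whichever way the results are read.

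Second, the sidedness of the sample-size alpha is inferred. Other formulas at one-sided 0.05 give other sizes: 116 per group with a score variance, 126 with a continuity correction. The inference stands because the plain formula matches exactly, but it remains an inference. If two-sided 0.05 was intended, 108 per group falls short of 80% power.

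Third, the odds-ratio comparison must be like for like, and it uses unadjusted analyses while the planned model adjusts for age, gender and severity. Compared at the same level, the odds-ratio rule is still weaker. The adjusted model was not simulated, so the exact gap for it is not known.

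Fourth, the text is in the past tense and gives enrolment as April 2015 to March 2018. A rule written now may itself come after the data, and choosing 90% over 95% is partly judgement. This does not rescue the plan, but it affects how the fix should be labelled.

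**Conclusion.** The concern holds. As written, the plan tests equality on the odds-ratio scale, while the sample size was set for non-inferiority on the risk-difference scale. The missing items are the estimate, the confidence level and the decision rule. The confidence level alone moves the power at 108 per group from about 80% (90% interval) to 68-71% (95% interval).

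This rests on several assumptions:

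- the 11% is absolute, the only reading examined that gives 216;
- the single dose is the arm under test, since the documents do not name a reference group;
- 108 per group all reach the day-6 call, as no allowance for loss is stated;
- the calculations are unadjusted.

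The opening part of the document was not available for this review, so a rule stated there could not be seen. The point must be fixed because it concerns the trial's main conclusion.

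**What to change.** Amend the Analytic Plan to state:

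1. Return visit for asthma is the primary outcome.
2. The estimate is the absolute risk difference, single dose minus two dose, by Newcombe, Miettinen-Nurminen, or standardisation from the logistic model already planned.
3. The limit is 11 absolute percentage points.
4. The decision uses the upper limit of a two-sided 90% interval (one-sided 0.05), the level that yields 216, with the 95% interval printed beside it. Non-inferiority is concluded only if that upper limit is below 11 points.
5. A non-significant odds ratio is not evidence of non-inferiority; odds ratios remain as secondary summaries.
6. The analysis population for this comparison. Intention-to-treat is mentioned only in the sentence on severity comparisons.

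If the 95% interval is preferred for the decision, to agree with the two-tailed convention, restate the power as about 68-71%. If the rule is written after results have been seen, label it post hoc and show both intervals.

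**Cost.** Revised wording and one extra estimate from data already collected. The 90% rule keeps 78-81% power at 108 per group with full follow-up, so it needs no extra patients. Reaching 80% with a 95% interval would take 137 per group (274 in total) by the normal formula, or about 142 per group with Newcombe. Some results otherwise reported as showing no difference will become inconclusive, and some readers will find a 5% one-sided error lenient.
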